1.2 Secondary Objective

A secondary objective of this study is to determine if adherence with blood pressure monitoring is associated with change in blood pressure during the study period and to determine which individual factors are associated with adherence.

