4.3 Inclusion Criteria

1. Adult, age ≥ 18 years
2. History of ischemic stroke, intraparenchymal hemorrhage, or high risk TIA (defined by ABCD2 ≥ 4) with the past 5 years prior to enrollment
3. Hypertensive at time of screening, defined by SBP >140 mm Hg or DBP >90 mm Hg
4. Enrollment must occur within 30 days of study screening
5. Must own a smart phone capable of interacting with the connected blood pressure cuff (Apple iPhone 3GS or higher; Android 4.0 or higher with Bluetooth connectivity)
6. Must be able to identify at least one adult (≥ 18) with internet access and/or a smart phone with text messaging capability who could serve as a social support person.
7. Willingness and ability to sign informed consent by patient

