4.6 Subject Recruitment

4.6.1 Participant Screening and Recruitment

Potential study participants will be identified from the inpatient stroke service at the Hospital of the University of Pennsylvania and the outpatient neurology clinic at the Hospital of the University of Pennsylvania. Additionally, the neurology residents and the stroke physicians at the Hospital of the University of Pennsylvania will be

informed of the study and provided with contact info for study personnel to refer eligible outpatients. The attending physician caring for the patient will be informed of eligible patients prior to enrollment. Screening visits may include an inpatient admission for stroke or TIA or any routine outpatient clinic visits in which blood pressure is measured. Inpatients who are considered for the study can only be enrolled if they are being discharged to home, and enrollment should occur on the date of discharge. Patients discharged to an inpatient rehabilitation hospital or skilled nursing facility are excluded from participation.

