5.2 Design

This is a single center randomized trial designed to assess the effectiveness of a social intervention to improve adherence with home blood pressure monitoring. Computer-based block randomization (block size=4) will be used to maintain relatively equal numbers of subjects in both arms of the study. This study will provide important preliminary data for future studies, which will use behavioral incentives to improve adherence to home blood pressure monitoring and titration of antihypertensive therapy.

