7. STUDY PROCEDURES

7.1 ENROLLMENT

At the time of enrollment the following data will be collected: Age, sex, race, ethnicity, handedness (left arm dominate, right arm dominate), date of stroke, etiology of stroke (large vessel disease, small vessel disease, cardioembolic, other defined etiology, cryptogenic), past medical history (including prior history of: hypertension, diabetes, hyperlipidemia, atrial fibrillation, congestive heart failure, coronary artery disease and/or myocardial infarction, chronic kidney disease, peripheral artery disease, stroke prior to the enrolling event, and other), current medications, smoking history (current, former, never smoker), employment status (currently employed, disabled, retired), living situation (lives alone yes/no, if no, number of people and relationship of people living in the home), annual household income (<\$20,000, \$20,000-39,999, \$40,000-64,999, \$65,000-104,999, \$105,000+), insurance status (private health insurance, medicare, medicaid, none), primary care provider (yes/no), cardiologist (yes/no), nephrologist (yes/no). We will also obtain contact information for follow-up phone calls and for scheduling the 90 day visit. Social security numbers will be collected for subject reimbursement purposes.

Figure 1. Modified Rankin Scale

Modified Rankin Scale	
0	No symptoms
1	No disability; able to carry out all previous activities despite some symptoms
2	Slight disability; unable to carry out all previous activities but able to look after own affairs
3	Moderate disability; requires some help but able to walk unassisted
4	Moderately severe disability; unable to attend to own bodily needs and unable to walk unassisted.
5	Severe disability; requires constant nursing care and attention, bedridden.

Study Measurements at enrollment

- Upper arm circumference. Measured using a tape measure in the mid-portion of the upper arm. Circumference <9" or >17" is an exclusion criteria.
- Mini-Mental Status Examination (MMSE) – the MMSE is a brief, standardized cognitive assessment. Subjects will be excluded if they score ≤ 20 on the MMSE, which corresponds to moderate or severe dementia.

2. Modified Rankin Scale (mRS). The mRS is a 5 point scale which ranges from no disability to severe disability (figure 1). It is assessed using a brief, structured interview. Study personnel will be trained and certified in the use of the mRS. Subjects with mRS >2 are excluded.

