We will compare secondary outcomes across study arms including number of calls to the study team, number of physician visits, number of emergency department visits, number of changes in antihypertensive medications, and the patient perception of: study protocol, utility of blood pressure monitoring, and blood pressure control. We will also determine the relationship between adherence to blood pressure monitoring and change in blood pressure during the study period. For this analysis, we will first determine the average adherence in the study population. We will compare the change in blood pressure in those with above average adherence to those with below average adherence. This will be done in the full study population and then stratified by study arm. In an exploratory analysis multivariable regression will be utilized to determine which factors were associated with a high level of adherence to the study protocol, defined as adherence above the study median. We will investigate the following variables in a univariate analysis: age, sex, race, ethnicity, income, social support in the home, employment status, MMSE score, NIHSS, and modified Rankin Scale. Variables in the univariate analysis with $p < 0.10$ will be incorporated into a multivariable logistic regression model. We will test for an interaction between the social incentive and the variables in the multivariable model.

9. Data Handling and Record Keeping

9.1 Confidentiality.

- Paper-based records will be kept in a secure location and only be accessible to personnel involved in the study.
- Computer-based files will only be made available to personnel involved in the study through the use of access privileges and passwords.
- Prior to access to any study-related information, personnel will be required to sign statements agreeing to protect the security and confidentiality of identifiable information.
- Whenever feasible, identifiers will be removed from study-related information.

- A Certificate of Confidentiality will be obtained, because the research could place the subject at risk of criminal or civil liability or cause damage to the subject's financial standing, employability, or liability.
- A waiver of documentation of consent is being requested, because the only link between the subject and the study would be the consent document and the primary risk is a breach of confidentiality. (This is not an option for FDA-regulated research.)

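### The adherence versus BP-change comparison is unadjusted, although entry runs from discharge day to 5 years after the event; add a model adjusted for time since event

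*Combined protocol and SAP*

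**What the plan says.** All references are to the combined protocol and SAP.

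- **Objective.** Section 1.2 sets out to "determine if adherence with blood pressure monitoring is associated with change in blood pressure during the study period" and to find which individual factors go with adherence.
- **Entry window.** Section 4.3 accepts a qualifying event "with the past 5 years prior to enrollment". Section 4.6.1 says of recruitment: "Screening visits may include an inpatient admission for stroke or TIA or any routine outpatient clinic visits in which blood pressure is measured". For inpatients, "enrollment should occur on the date of discharge".
- **Randomization.** Section 5.2: "Computer-based block randomization (block size=4) will be used to maintain relatively equal numbers of subjects in both arms of the study". No stratification factor is named.
- **Baseline data.** Section 7.1 collects "date of stroke, etiology of stroke" and an enrollment BP averaged over three readings. It lists neither a TIA date nor the recruitment setting as a data item.
- **BP change.** Section 8 takes the mean home BP in the first and last 7 days of monitoring.
- **Adherence and BP change.** Section 8: "We will compare the change in blood pressure in those with above average adherence to those with below average adherence". This is done in all subjects and then by arm, with no covariate named.
- **Adherence factors.** The exploratory model in section 8 draws on ten candidates: "age, sex, race, ethnicity, income, social support in the home, employment status, MMSE score, NIHSS, and modified Rankin Scale". Those with univariate p<0.10 go forward. Time since event is not a candidate.

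**The concern.** The comparison by adherence is observational, even though it sits inside a randomized trial. Subjects choose how often to measure, so any baseline characteristic tied both to that choice and to the later course of BP will distort the comparison.

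The eligibility rules build in one such candidate. For a subject enrolled at discharge, the first week of home readings is the first week out of hospital. For another subject, the same week may fall years after the event. The two may differ in BP course, in intensity of follow-up and in motivation to monitor. If recent subjects monitor more and their BP falls further for other reasons, the plan reports an association that monitoring did not produce. If they monitor less, a real association may be hidden. Repeating the comparison by arm does not help, because adherence is not randomized within an arm either.

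The protocol intends the results to inform later trials of home monitoring and treatment titration, so a misread association could carry forward.

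The factor list raises a separate and smaller matter. Section 1.2 asks which factors relate to adherence, and time since event, which varies widely by design, cannot be found there because it is not a candidate.

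**Working it through.** **The plan's own figure.** The plan states no effect size, SD or power for this analysis. The 90 subjects in section 4.2 were chosen for the primary arm comparison. With 45 per arm and a 0.30 difference, the comparison of means named there implies an SD of 0.30 / [(1.960 + 0.842) × √(2/45)] = 0.51. Alternatively, a continuity-corrected comparison of 50% with 80% gives 45 per arm. The figure of 90 can be reproduced, and this point does not affect it.

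**Bias if adherence has no effect on BP.** Let e be the share of recent-event subjects and D their extra 90-day systolic fall unrelated to monitoring. Let p₁ and p₀ be the probabilities of above-average adherence in recent and remote subjects. Then:

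- P(high) = e·p₁ + (1−e)·p₀
- P(recent | high) = e·p₁ / P(high)
- P(recent | low) = e·(1−p₁) / (1−P(high))
- Bias = D × [P(recent | high) − P(recent | low)]

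Every input is an assumption, because the documents give none of them: e from 20% to 50%, D from 5 to 15 mm Hg, and p₁ and p₀ as shown.

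| e | p₁ vs p₀ | P(recent given high) − P(recent given low) | D (mm Hg) | Bias (mm Hg) |
|---|---|---|---|---|
| 50% | 50% vs 50% | 0.500 − 0.500 = 0 | any | 0 |
| 20% | 60% vs 45% | 0.250 − 0.154 = 0.096 | 5 | +0.5 |
| 50% | 60% vs 40% | 0.600 − 0.400 = 0.200 | 10 | +2.0 |
| 50% | 70% vs 40% | 0.636 − 0.333 = 0.303 | 15 | +4.5 |
| 20% | 40% vs 55% | 0.154 − 0.250 = −0.096 | 5 | −0.5 |
| 50% | 40% vs 55% | 0.421 − 0.571 = −0.150 | 15 | −2.3 |

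Positive means a larger apparent fall in the high adherers. The range is lopsided only because the largest positive case assumes a 30-point adherence gap and the reverse cases a 15-point gap. Reversing the 30-point gap (40% vs 70%, e = 50%, D = 15) gives (0.364 − 0.667) × 15 = −4.5. The range therefore says nothing about which direction is likelier.

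**Effect on a 5% test.** Assume 45 subjects in each adherence group and an SD of change of 12 to 15 mm Hg. Then SE = SD × √(2/45) = 2.53 to 3.16, and the rejection probability is 1 − Φ(1.96 − b/SE) + Φ(−1.96 − b/SE) for bias b.

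- b = 2: about 12% (SD 12) or 10% (SD 15)
- b = 4.5: about 43% (SD 12) or 30% (SD 15)

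A split at the average need not give equal groups, and subjects with under 14 days of monitoring drop out of the main BP-change analyses, so 45 per group is a best case.

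**The case against.** The strongest reply is that the plan claims nothing causal. Section 1.2 speaks of an association, and an unadjusted association is a legitimate thing to report. That stands. A reader might infer that the plan attributes BP change to monitoring, but no passage says so. What remains is that an association open to this distortion is of little use to later trials when the data to examine it are at hand.

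Second, the contrast between recent and remote subjects is narrower than it first looks. All must have SBP >140 or DBP >90 mm Hg at screening, so remote subjects are also uncontrolled and may also have treatment changed. Moderate disability or worse, cognitive impairment and facility residence are excluded. BP change is measured between home readings, not from an inpatient value. These points weaken the case for a large D but do not exclude confounding.

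Third, time since event is only one omitted variable. Baseline BP, age, income and medication changes could matter as well. This is correct, and it is why the model below includes enrollment BP and why its result would still not be causal.

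Fourth, a reader might infer that leaving time since event off the factor list also produces a false BP effect. It cannot: the outcome of that model is high adherence, not BP. The omission only leaves part of section 1.2 less fully answered.

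**Conclusion.** The point holds as a moderate one. The comparison takes a non-randomized exposure, adjusts for nothing and is merely repeated by arm, in a population whose time since event runs from discharge day to 5 years. It is confounded if time since event is related to both adherence and 90-day BP change. Whether that is so, and in which direction, cannot be learned from the documents. Under the assumed inputs the bias runs from about −2 to +4.5 mm Hg, including zero, and these figures illustrate rather than estimate it.

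A reader might go further and conclude that the trial's main results are compromised. The documents do not support that. The comparisons of adherence and BP change between arms rest on randomization and are not biased in expectation by time since event, although chance imbalance is possible without stratification. The point touches one secondary analysis and one exploratory analysis in a pilot.

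**What to change.** In section 8:

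1. Keep the above- versus below-average split, labelled unadjusted and descriptive.
2. Add a linear regression of BP change on adherence, adjusted for arm, enrollment BP and time since the qualifying event. Derive the last from the collected event date, and add the TIA date to section 7.1 for TIA subjects. Keep the existing language of association.
3. Separately, add time since event to the candidate adherence factors.
4. Leave recruitment setting to a sensitivity analysis. It overlaps heavily with time since event, since inpatients enrolled at discharge sit near zero, and it would have to be recorded as a data item.

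The cost is a few sentences, one model, one date field and a few degrees of freedom among at most 90 subjects. The factor model gains an eleventh candidate, with only about 45 subjects above the median. Residual confounding remains, and the report should say so.

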9.2 Source Documents

Source documents are all information, original records of clinical findings, observations, or other activities in a clinical trial necessary for the reconstruction and evaluation of the trial. Source data are contained in source documents. Examples of these original documents, and data records include: hospital records, clinical and office charts, laboratory notes, memoranda, subjects' diaries or evaluation checklists, pharmacy dispensing records, recorded data from automated instruments, copies or transcriptions certified after verification as being accurate and complete, microfiches, photographic negatives, microfilm or magnetic media, x-rays, subject files, and records kept at the pharmacy, at the laboratories, and at medico-technical departments involved in this research.

Trained members of the research team may review source documents at the time of enrollment/consent in order to ensure patient eligibility. Necessary data from the source documents will be recorded on the case report form. Copies of source documents will not be needed for this study.

9.3 Case Report Forms

The study case report form (CRF) is the primary data collection instrument for the study. Hard copy of all case report forms will be kept secure in a locked cabinet accessible to the study primary investigator and study coordinator. Data for this study will also be stored in an electronic database via the Way to Health platform. Way to Health is secure and HIPAA compliant. Data contained within Way to Health will only be accessible to appropriately trained study personnel.

9.4 Records Retention

It is the investigator's responsibility to retain study essential documents for at least 2 years after the last approval of a marketing application in their country and until there are no pending or contemplated marketing applications in their country or at least 2 years have elapsed since the formal discontinuation of clinical development of the investigational product.

We will retain all case report forms and the electronic databases for a minimum of two years after completion of the study.

Personal identifiers will not be released to other investigators under any circumstances. If at any time the data is to be shared with other investigators for future research, it will be de-identified prior to release. The data collected in this study will not become a part of the subject's permanent record.

9.5 Subject Privacy/Protected Health Information

The following protected health information (PHI) will be collected:

- Name
- Address
- Social Security Number

- Medical record number
- Phone number
- Email address
- Medical history
- Current and past medications or therapies
- Information from a physical examination that generally also includes blood pressure reading, heart rate, breathing rate and temperature
- Information from laboratory and imaging tests such as echocardiograms, MRI and CT scans.

Collected PHI will be recorded on the case report form, which will be secured as detailed above. It will otherwise not be disclosed to anyone outside of key study personnel.

The HIPPA authorization for this study will be incorporated into the informed consent form. In the event that a subject revokes authorization to collect or use PHI, the investigator, by regulation, retains the ability to use all information collected prior to the revocation of subject authorization. For subjects that have revoked authorization to collect or use PHI, attempts will be made to obtain permission to collect at least vital status (i.e. that the subject is alive) at the end of their scheduled study period.

9.6 Tissue Specimens

Not applicable

9.7 Genetic Testing

Not applicable

10. RISK/BENEFIT ASSESSMENT

10.1 Potential Study Risks

There are no risks associated with the blood pressure monitor used in this study. The study team will take every possible step to maintain your privacy, including using password protected files and minimizing the use of identifying information on study documentation, but whenever private health information is collected there is always a small risk that a breach of confidentiality could occur.

10.2 Potential Study Benefits

This study has the potential to benefit all subjects. Hypertension is the most important modifiable risk factor for stroke and an important risk factor for myocardial infarction, chronic kidney disease, and other serious medical conditions. Study education about the importance of hypertension, goal blood pressure levels, and regular monitoring of blood pressure may lead to improved blood pressure control in subjects, which in turn has the potential to lower the risk of serious medical conditions, including heart attack and stroke. There is also a potential societal benefit, as this study will provide important insights into adherence with home monitoring in patients with cerebrovascular disease and may be useful for future larger studies which combine home monitoring with therapeutic interventions to lower blood pressure with the goal of reducing the risk of future stroke.

10.3 Alternatives to Participation

Participation in this research study is voluntary. Subjects may choose not to participate; their decision to participate or not will not affect their regular medical care in any way.

10.4 Risk/Benefit Assessment

Considering the minimal risk to participants and the potential benefit both to individual participants and to society, the risk to benefit ratio is favorable.

11. Data and Safety Monitoring

This study will be monitored by:

- Principal Investigator
- Sponsor or contract research organization
- NCI sponsored cooperative group
- Cancer Center (if mandated by CTSMRC)
- Medical monitor
- Safety monitoring committee
- Data and safety monitoring board

11.1 Definitions

Adverse Event

An **adverse event** (AE) is any symptom, sign, illness or experience that develops or worsens in severity during the course of the study. Intercurrent illnesses or injuries should be regarded as adverse events. Abnormal results of diagnostic procedures are considered to be adverse events if the abnormality:

- Results in study withdrawal
- Is associated with a serious adverse event
- Is associated with clinical signs or symptoms
- Leads to additional treatment or to further diagnostic tests
- Is considered by the investigator to be of clinical significance

Serious Adverse Event

Adverse events are classified as serious or non-serious. A **serious adverse event** is any AE that is:

- Fatal
- Life-threatening
- Requires or prolongs hospital stay
- Results in persistent or significant disability or incapacity
- A congenital anomaly or birth defect
- An important medical event

Important medical events are those that may not be immediately life threatening, but are clearly of major clinical significance. They may jeopardize the subject, and may require intervention to prevent one of the other serious outcomes noted above. For example, drug overdose or abuse, a seizure that did not result in in-patient hospitalization or intensive treatment of bronchospasm in an emergency department would typically be considered serious.

All adverse events that do not meet any of the serious criteria will be regarded as **non-serious adverse events**.

Adverse Event Reporting Period

The study period during which adverse events must be reported is defined as the period from the initiation of any study procedures to the end of the study treatment follow-up. For this study, the study treatment follow-up is defined as 90 days from enrollment, or at the final study visit, whichever comes first.

Preexisting Condition

A preexisting condition is one that is present at the start of the study. A preexisting condition should be recorded as an adverse event if the frequency, intensity, or the character of the condition worsens during the study period.

General Physical Examination Findings

At screening, any clinically significant abnormality should be recorded as a preexisting condition. At the end of the study, any new clinically significant findings/abnormalities that meet the definition of an adverse event will be recorded and documented as an adverse event.

Post-study Adverse Event

All unresolved adverse events will be followed by the investigator until the events are resolved, the subject is lost to follow-up, or the adverse event is otherwise explained. At the last scheduled visit, the investigator should instruct each subject to report any subsequent event(s) that the subject, or the subject's personal physician, believes might reasonably be related to participation in this study. The investigator should notify the FDA and IRB of any death or adverse event occurring at any time after a subject has discontinued or terminated study participation that may reasonably be related to this study.

Hospitalization, Prolonged Hospitalization or Surgery

Any adverse event that results in hospitalization or prolonged hospitalization will be documented and reported as a serious adverse event unless specifically instructed otherwise in this protocol. Any condition responsible for surgery will be documented as an adverse event if the condition meets the criteria for an adverse event.

Neither the condition, hospitalization, prolonged hospitalization, nor surgery are reported as an adverse event in the following circumstances:

- Hospitalization or prolonged hospitalization for diagnostic or elective surgical procedures for a preexisting condition. Surgery should **not** be reported as an outcome of an adverse event if the purpose of the surgery was elective or diagnostic and the outcome was uneventful.
- Hospitalization or prolonged hospitalization required to allow efficacy measurement for the study.
- Hospitalization or prolonged hospitalization for therapy of the target disease of the study, unless it is a worsening or increase in frequency of hospital admissions as judged by the clinical investigator.

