4.6.7 Follow-up Period

Participants will have a follow-up phone call at 48-72 hours after enrollment and either a phone or computer based encounter 30 days +/- 3 days after enrollment and an in-person visit at 90 days +/-7 days. Participation will be completed after the day 90 visit.

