5.3 Study Duration

Individual subjects will be in the study for a total of 90 days. They will receive a telephone call at 48 hours and either a computer based or telephone based interview at 30+/- 3 days and then will have an in-person visit at 90+/-7 days.

Total study duration is expected to last approximately 2 years. We expect to enroll about 6 subjects per month and should reach our target of 90 patients by 15 months. The final follow-up visit will occur 3 months after the last patient is enrolled. Data collection and analysis will be completed in the subsequent 6 months for total study duration of 24 months.

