Subjects who do not complete the online form will be contacted by telephone in order to assess the same information.

7.4 90 Day Follow-up Visit

At 90 +/- 7 days from enrollment the subject will be seen for an in-person visit. They will be asked to return the blood pressure monitor at that time and be screened for adverse events. Outcomes will again be assessed. Blood pressure readings and adherence to twice daily blood pressure monitoring will be collected automatically via Way to Health and will not need to be assessed during this in-person visit. Secondary outcomes assessed will include:

- TIA or stroke since 30 day phone call
- Number of physician visits since 30 day phone call (Primary care, cardiology, other)
- Number of emergency department visits since 30 day phone call and reason for each visit
- Number of changes in antihypertensive medications since 30 day phone call (dose adjustment and/or addition of a new agent)
- Patients perception of blood pressure monitoring device and study protocol ease of use (very difficult, moderately difficult, mildly difficult, easy to use)

- Patients perception of the utility of blood pressure monitoring (very useful, moderately useful, mildly useful, not useful)
- Patients perception of blood pressure control (adequately controlled, not adequately controlled)

Heart rate and blood pressure will be assessed in the non-dominant arm using an automated cuff. This will be repeated 3 times and averaged to determine final blood pressure. The modified Rankin Scale and NIHSS will also be assessed, as described in section 7.1. Research personnel assessing both the mRS and the NIHSS will be trained and certified in its use. Finally, for each subject we will tabulate the number of telephone calls to the study team initiated by the subject and the purpose of the call (blood pressure reading high/low, technical difficulty with device, other).

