8. STATISTICAL ANALYSIS

Demographics and past medical history variables will be summarized for all subjects using means or medians as appropriate for continuous variables and proportions for categorical variables. We will compare the two study arms using Student's t-test or Wilcoxon rank sum as appropriate for continuous variables and χ^2 test for categorical variables.

The primary outcome measure is adherence with blood pressure monitoring during the study period. Adherence will be defined by dividing the number of successfully completed BP measurements (numerator) by the expected number of BP measurements (denominator). The expected number of BP measurements is the number of days that the subject is in the study multiplied by 2. Most subjects will be enrolled in the study for 90 days and will therefore be expected to check their BP 180 times. Adherence in this case is the number of completed BP measurements divided by 180. The 90-day follow-up visit has a window of +/- 7 days, so for subjects that complete the study protocol the denominator will be adjusted accordingly. Subjects whom withdrawal from the study and/or stop monitoring their BP before the 90-day follow-up visit will remain in the analysis. These subjects will be considered non-adherent for all BP measurements after they cease taking measurements and the denominator will be set at 180. As an example, if a subject checks their BP 60 times in the first 75 days of the study and then ceases all BP measurements, adherence will be calculated as $60/180=33.3\%$. After adherence has been calculated for all subjects we will evaluate the distribution of adherence for normality and compare adherence between the two study arms using Student's t-test or Wilcoxon rank sum as appropriate. A sample size of 90 will give us 80% power to detect a 30% difference between groups with $\alpha=0.05$.

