11.2 Recording of Adverse Events

At each contact with the subject, study personnel will seek information on adverse events by specific questioning and, as appropriate, by examination. Information on all adverse events will be recorded immediately in the source document, and in the appropriate adverse event module of the case report form (CRF). All clearly related signs, symptoms, and abnormal diagnostic procedures with their results will be recorded in the source document, grouped under one diagnosis.

All adverse events occurring during the study period will be recorded. The clinical course of each event should be followed until resolution, stabilization, or until it has been determined that the study treatment or participation is not the cause. Serious adverse events that are still ongoing at the end of the study period must be followed up to determine the final outcome. Any serious adverse event that occurs after the study period and is considered to be possibly related to the study treatment or study participation should be recorded and reported immediately.

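### The adverse-event reporting period in 11.1 closes no later than day 90, but participation and the visit that screens for events can run to day 97, so the duty to report in between is unclear

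*Combined protocol and SAP*

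**What the plan says.** Section 11.1, under its reporting-period heading, starts the period in which adverse events must be reported at the first study procedure and ends it with study treatment follow-up. It then fixes that end: "the study treatment follow-up is defined as 90 days from enrollment, or at the final study visit, whichever comes first".

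The visit schedule is looser. Section 4.6.7 calls for "an in-person visit at 90 days +/-7 days" and adds: "Participation will be completed after the day 90 visit". Section 7.4 gives the same window ("At 90 +/- 7 days from enrollment the subject will be seen for an in-person visit") and says of subjects at that visit: "They will be asked to return the blood pressure monitor at that time and be screened for adverse events". The table in 7.5 also marks adverse-event screening at day 90 +/- 7. Section 5.3 repeats the window, although the same section also says: "Individual subjects will be in the study for a total of 90 days".

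Section 11.2 contains three relevant rules. Staff are to ask about adverse events at every contact and record information on all of them at once. Next, "All adverse events occurring during the study period will be recorded". Lastly, serious events after the study period must be recorded and reported if possibly related to the study. Section 11.3 sends all serious events to the IRB whether or not they are related, and states no end date.

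**The concern.** Because 11.1 takes the earlier of two dates, reporting closes at day 90 for everyone whose final visit falls on days 91 to 97. Those subjects are still participants. They may still hold the cuff, which is returned at the visit. Their adherence denominator follows the actual visit day, since section 8 notes that "The 90-day follow-up visit has a window of +/- 7 days" and adjusts for it.

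Section 7.4 also counts TIA or stroke, and emergency department visits, from the 30-day contact up to the visit itself, with no cut-off at day 90. A stroke on day 93 disclosed at a day-95 visit would be a collected outcome, yet it would lie outside the period in which 11.1 requires adverse events to be reported.

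What is at stake is consistent safety reporting. Two coordinators could handle identical events differently, each with support in the text. Under 11.4 safety oversight rests with the principal investigator and there is no data and safety monitoring board, so the written rule carries more weight.

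**Working it through.** The plan gives no figure of its own to reproduce. The check is date arithmetic, followed by a comparison of the reporting rules.

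**Inputs**
- Final visit day V: 83 to 97 (90 - 7 to 90 + 7; sections 4.6.7, 5.3, 7.4, 7.5).
- End of the reporting period: min(90, V) (section 11.1).
- End of participation: after the visit, so day V (section 4.6.7).
- Planned enrolment: 90 (section 4.2).

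**Gap per subject**

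Gap = V - min(90, V) = max(0, V - 90).
- V = 83 to 90: gap 0.
- V = 91: gap 1 day.
- V = 97: gap 97 - 90 = 7 days, the maximum, or 7/97 = 7% of that subject's time in the study.

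**Range over the study.** The documents do not say how visit days will be distributed. The limits, if all 90 subjects attend, are:
- every visit by day 90: 0 person-days;
- every visit on day 97: 90 x 7 = 630 person-days.

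As an illustration between these limits, assume visits spread evenly over the 15 days from 83 to 97 and full attendance:
- share of subjects with a gap: 7/15 = 47%;
- mean gap: (1 + 2 + ... + 7)/15 = 28/15 = 1.87 days;
- total: 1.87 x 90 = 168 person-days (28/15 x 90 exactly).

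These figures count days outside one definition. They do not count missed events.

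**Which events lack a clear duty between day 90 and a later visit**

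| Event after day 90, before the visit | Reporting period in 11.1 | Other rules | Result |
|---|---|---|---|
| Serious, possibly related | Outside | 11.2 requires recording and reporting; 11.3 requires submission | Covered |
| Serious, judged unrelated | Outside | 11.3 requires submission with no end date, but may be read as limited by 11.1 | Two readings |
| Non-serious | Outside | 11.2 has staff ask and record at each contact, but also ties recording to the study period | Probably recorded; duty unclear |

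The post-study rule in 11.1 does not settle the last two rows. It applies once a subject has discontinued or ended participation, and it concerns related events only. A subject waiting for a day-95 visit is still participating.

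**The case against.** A reader might infer that up to a week of adverse events goes unreported, or that after day 90 section 11.2 requires nothing beyond serious events judged possibly related. The documents do not support either inference. Section 11.2 opens with a rule that has no day-90 limit: events are sought at each contact and information on all of them is recorded. A visit on days 91 to 97 is such a contact, and screening is scheduled at it. Section 11.3 submits every serious event without an end date. Section 11.1 itself treats events leading to hospitalization as serious and reportable, with listed exceptions, and defines an adverse event by reference to the course of the study. The day-93 stroke is collected under 7.4 in any case. At most, its status as a reportable adverse event is ambiguous.

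It can also be said that day 90 matches the nominal duration in 5.3, that the study is described as minimal risk (10.4), and that section 8 plans no adverse-event analysis, so no study result changes.

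Most of this stands, and it limits the point to an unclear duty. It does not remove the conflict. Screening finds an event but does not place it inside the period in 11.1. The general recording rule in 11.2 sits beside a sentence tied to the study period. The nominal 90 days in 5.3 appears in the same section as the +/- 7 day window.

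**Conclusion.** The sections conflict, and the point holds as an inconsistency in safety reporting. For subjects whose final visit falls on days 91 to 97, non-serious adverse events in the 1 to 7 days before that visit lie outside the reporting period that 11.1 defines. Serious events judged unrelated do so on one reading of 11.1 against 11.3. Possibly related serious events are covered.

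The maximum of 7 days follows directly from the text. The 47% and the 168 person-days do not: they assume even visit timing and full attendance, and the documents establish neither. Sample size, power and type I error are unaffected. This is a minor point, worth correcting because the correction is so small.

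**What to change.** In 11.1, replace the earlier-of-two-dates wording so that the reporting period runs from the first study procedure through the final study visit. For a subject with no final visit, state a fixed end; the end of the visit window, day 97, is the natural choice. Sections 11.1, 11.2, 11.3 and 7.4 would then cover the same period.

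For every subject who attends, the end of the period becomes V and the gap becomes V - V = 0 days. The cost is one sentence in the protocol and possibly a few more event reports. No visit, measurement or analysis changes.
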